Measurements and calculations by 2D echo will include left ventricular end systolic and end-diastolic dimensions, left ventricular ejection fraction by Simpson's method, left atrial volume, severity of mitral and tricuspid regurgitation, velocity of tricuspid regurgitation, diameter of inferior vena cava and its variability with respirations, and right ventricular function by tricuspid annular plane systolic excursion.

Measurements by right heart catheterization will include right atrial pressure, right ventricular systolic and end diastolic pressure, pulmonary arterial systolic, diastolic, and mean pressure, and pulmonary capillary wedge pressure. Cardiac output and cardiac index will be calculated both by Fick and thermodilution methods.

The majority of study information will be collected from routine care for standard clinical indications.

Primary outcome

6 minute walk distance

Secondary outcomes

Percent of change of pulmonary arterial pressures (systolic, diastolic, and mean) and pulmonary vascular resistance from the baseline

Percent of change of cardiac index from the baseline

Percent of change in tricuspid annular plane systolic excursion

3. Objectives

Primary Objective:

The primary objective of this study is to determine whether sildenafil for treatment of HF with reactive PH can improve exercise tolerance measured by 6 minute walk distance

Secondary Objectives:

The secondary objectives of this study are to determine whether sildenafil for treatment of HF with reactive PH can improve hemodynamics, right ventricular function, or quality of life

4. Eligibility (include rationales for selecting or excluding particular cohorts)

Inclusion criteria:

[figure not shown]
- ≥ 18 years of age
- Known chronic heart failure appropriately treated with angiotensin converting enzyme antagonists, angiotensin receptor blockers, and beta blockers, unless contraindicated, not indicated, or poorly tolerated
- Indications for right heart catheterization, other than for biopsy
- Pulmonary artery mean pressure >25 mm Hg, pulmonary capillary wedge pressure >15 mmHg, and pulmonary vascular resistance >3 WU as measured by right heart catheterization within 3 days of planned randomization

Exclusion criteria:

- Hypersensitivity, allergy, or intolerable side effects of sildenafil

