Primary and secondary endpoints are as noted above. Patients will be randomized to treatment versus placebo in a 1:1 ratio using permuted blocks of variable size, to which the principal investigator (and the patients themselves) will be blinded. Planned sample size is 64, as described below. Data will be analyzed on an intent-to-treat basis, as described below. An interim analysis will also take place after data have been acquired for (approximately) 32 subjects, using a temporary alpha of 0.01 to mitigate inflation of Type I error probability due to multiple testing. Results of interim data analysis will be shared with Data Safety Monitoring Board, which will advise the principal investigator on whether to continue with the study.

Planned sample size of 64 will provide nearly 80% power, using the final alpha of 0.05, to detect a difference between groups on a numerical outcome variable for which the effect size is approximately 0.7, in the sense that a typical person in the treatment group would be approximately seven-tenths of one standard deviation better than a typical person in the control group. This is slightly greater than the effect size of approximately 0.6 observed by Mathai and colleagues for the exercise endpoint, but we anticipate being able to reduce variability by considering change scores from baseline to 3 months rather than just the final results at 3 months.

Each numerical outcome variable will be examined for approximate normality, and appropriate corrective action (e.g., log transformation prior to further data analysis) will be considered if approximate normality is untenable. A linear mixed model will be fit relating each outcome variable to group (between-subjects factor: treatment vs. placebo) and time (within-subjects factor: baseline vs. 3 months), with random effects for subjects and embedded linear contrasts to compare groups on change from baseline to 3 months. Although randomization is anticipated to balance groups on demographic and clinical characteristics, in the unlikely event that groups are imbalanced we can modify the linear mixed modeling to adjust for any covariates on which groups are imbalanced. Loss to follow-up is anticipated to be small, but in the unlikely event of more than 10% attrition from either group we can employ multiple imputation or another method for handling missing data. Groups will be compared on adverse events (e.g., re-hospitalization) using Fisher's exact test.

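### Secondary endpoints are defined as percent changes, but the planned model tests absolute change without baseline adjustment and leaves the effect scale to a normality check

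*Combined protocol and SAP*

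**What the plan says.** In section 2 (Trial design), the list of secondary outcomes has three entries. The first is "Percent of change of pulmonary arterial pressures (systolic, diastolic, and mean) and pulmonary vascular resistance from the baseline"; the second entry reads "Percent of change of cardiac index from the baseline"; the third entry reads "Percent of change in tricuspid annular plane systolic excursion". All are relative to each patient's own starting value. The primary outcome, 6-minute walk distance, is not defined as a percent change.

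Section 6 (Statistical design in detail) takes the endpoints over unchanged and gives one analysis for all of them: "A linear mixed model will be fit relating each outcome variable to group" and to time ("within-subjects factor: baseline vs. 3 months"), with random subject effects and "embedded linear contrasts to compare groups on change from baseline to 3 months". On transformation, it offers as an example that "log transformation prior to further data analysis) will be considered if approximate normality is untenable", without a test or threshold. On covariates, it says that if imbalance appears, "we can modify the linear mixed modeling to adjust for any covariates on which groups are imbalanced"; the baseline value of the outcome is not named. Neither section says how percent change is to be computed or analysed.

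**The concern.** The endpoint and the analysis are on different scales. The two time levels are baseline and 3 months, and percent change has no informative baseline level, so the outcome in the model has to be the measured pressure, resistance, cardiac index or tricuspid excursion. The contrast is then a difference in mm Hg, WU, L/min/m² or mm.

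Absolute and relative effects are different quantities. A vascular resistance ratio of 0.8 is a fall of 0.7 WU from 3.5 WU but 1.6 WU from 8 WU. A fall of 1 WU is 29% of 3.5 and 12.5% of 8. Because the log option depends on how the trial data look, the quantity reported for each endpoint could be settled after the data are seen.

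The second issue is efficiency. Baseline enters only as a response level with a free group effect, so with complete data the contrast is a plain change-score comparison. That is usually less precise than adjusting for baseline, and at 32 per arm the loss can matter. This part applies to the walk distance too, because the same model serves every outcome.

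**Working it through.** **1. The plan's own power figure.** Inputs from section 6: 32 per arm, effect 0.7 SD, alpha 0.05 (taken as two-sided). The noncentral t with 62 df gives 78.7% and the normal approximation 80.0%. The plan's figure of nearly 80% reproduces and is not disputed.

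**2. What the planned contrast estimates.** With complete data the group-by-time contrast is (mean 3-month minus mean baseline on sildenafil) minus the same on placebo. On one simulated dataset resembling vascular resistance (32 per arm), the fitted mixed-model contrast was −0.9706, identical to the difference in mean absolute change (−0.9706 WU). The difference in mean percent change was −18.8 points. After log transformation the contrast was −0.2195, and exp(−0.2195) − 1 = −19.7%.

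A hand example shows that the two scales can disagree. Arm A has patients going 4→3 and 12→12 WU; arm B has 4→4 and 12→11.
- Mean absolute change: A (−1 + 0)/2 = −0.5; B (0 − 1)/2 = −0.5. The planned contrast is zero.
- Mean percent change: A (−25 + 0)/2 = −12.5%; B (0 − 8.3)/2 = −4.2%.

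**3. Power for vascular resistance.** The documents give no SD or baseline-to-3-month correlation r, so all inputs here are assumed: log-normal values, treated ratio 0.8, 32 complete pairs per arm, no truncation at the entry cut, two-sided 0.05, 40,000 runs per setting.

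| Log-SD | r | Percent change | Raw change (plan) | Log change | Raw ANCOVA | Log ANCOVA |
|---|---|---|---|---|---|---|
| 0.3 | 0.4 | 74 | 69 | 76 | 87 | 89 |
| 0.3 | 0.6 | 89 | 84 | 90 | 94 | 95 |
| 0.4 | 0.4 | 48 | 43 | 52 | 62 | 66 |
| 0.4 | 0.6 | 67 | 59 | 69 | 73 | 78 |
| 0.4 | 0.8 | 93 | 86 | 94 | 92 | 95 |
| 0.5 | 0.4 | 32 | 29 | 36 | 43 | 48 |
| 0.5 | 0.6 | 47 | 39 | 50 | 52 | 59 |
| 0.5 | 0.8 | 77 | 65 | 79 | 75 | 83 |

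At log-SD 0.3 with r = 0.8 all five are at least 98%, and at log-SD 0.2 all are at least 96%. Null rejection at 32 per arm was 4.7–5.3% for every method, so all five tests are valid. At log-SD 0.4, the percent-change and raw-change tests disagreed on significance in about 15% of simulated trials at r = 0.4 and 0.6, and in 9% at r = 0.8.

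With fewer complete pairs (log-SD 0.4, r = 0.6), raw change against log ANCOVA gave 59/78 at 32 per arm, 46/65 at 24 and 33/47 at 16.

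**4. An additive effect instead.** Assumed: normal pressure, mean 40, SD 10, fall of 5 mm Hg, 32 per arm.

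| r | Percent change | Raw change (plan) | Raw ANCOVA | Log ANCOVA |
|---|---|---|---|---|
| 0.4 | 39 | 44 | 57 | 54 |
| 0.6 | 55 | 59 | 68 | 65 |
| 0.8 | 85 | 88 | 90 | 88 |

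Here raw change beats percent change and raw ANCOVA beats log ANCOVA. No one scale is best for every endpoint. On a common scale, baseline adjustment was never lower in steps 3 and 4.

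**5. Walk distance.** With equal SDs σ at both times, the change-score variance is 2σ²(1 − r) and the ANCOVA residual variance is σ²(1 − r²). Their ratio, ANCOVA to change, is (1 + r)/2: 0.75 at r = 0.5, 0.85 at 0.7 and 0.95 at 0.9.

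Section 6 moves from an earlier study's effect of 0.6 to 0.7 on the ground that change scores will vary less. If 0.6 is in final-value SDs (an assumption), the change-score effect is 0.6/√(2(1 − r)) and the ANCOVA effect 0.6/√(1 − r²). Setting each to 0.7 means a variance factor of (0.6/0.7)² = 0.735. Change scores then need r ≥ 1 − 0.735/2 = 0.63, and ANCOVA needs r ≥ √(1 − 0.735) = 0.52. Power for change/ANCOVA at 32 per arm:
- r = 0.4: 58/73
- r = 0.5: 66/78
- r = 0.6: 75/84
- r = 0.8: 96/98

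If 0.7 is instead already in change-score SDs, ANCOVA raises power from 78.7% to 88.9%, 84.8% or 80.7% at r = 0.5, 0.7 or 0.9.

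**The case against.** The best defence is that the only contradiction lies in secondary endpoints, and that the planned contrast is an accepted, unbiased analysis under randomization. For the walk distance, plan and power agree: both are about change. The word absolute appears nowhere; percent change might be meant as a reporting format. The log option is named, would give a relative effect, and might well be triggered for skewed vascular resistance. Covariate adjustment is also foreseen and could include baseline.

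The mismatch has no one-way cost either. A constant ratio favours relative scales, and under an additive effect the planned contrast beats the stated endpoint (44% against 39% at r = 0.4). Much of the gain comes from baseline adjustment, not from aligning the scale: at log-SD 0.4 and r = 0.4, raw change to raw ANCOVA adds 19 of the 23 points. The simulation also ignores the entry requirement of vascular resistance above 3 WU. With that cut (assumed median 4 WU, log-SD 0.4), the gap between raw change and log ANCOVA is 20, 16 and 7 points at r = 0.4, 0.6 and 0.8, somewhat smaller than without it.

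Most of this stands and limits the size of the point. It does not remove it. The plan never says how percent change is analysed. The log and covariate options are discretionary and have no criterion. That the better scale depends on the form of the effect is a reason to fix it in advance. The entry cut narrows the gap without changing the order.

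**Conclusion.** The concern holds. That the endpoint definitions and the analysis do not match, and that the scale is not fixed, follows from the text and needs no assumption. The mismatch is confined to the secondary endpoints; the missing baseline adjustment affects the walk distance as well. Neither makes the planned test invalid.

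The size is uncertain because the documents give no SD, correlation or effect form. For vascular resistance at log-SD 0.4, moving from raw change to log ANCOVA adds 66 − 43 = 23, 78 − 59 = 19 and 95 − 86 = 9 points at r = 0.4, 0.6 and 0.8. Scale and baseline both contribute, in shares that depend on r and on the order in which they are changed. At low variability the gain almost vanishes. For the walk distance, the gain at r = 0.4 to 0.6 is 15 to 9 points if the quoted 0.6 is in final-value SDs.

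This should be changed, but it is not a fatal flaw. Confidence is medium, because every magnitude rests on assumed inputs.

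**What to change.** In section 6, make the primary analysis of each outcome, walk distance included, the 3-month value adjusted for its baseline value, or the equivalent mixed model with a common baseline mean in both arms. Do this regardless of observed imbalance.

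Fix one effect scale per endpoint before any unblinding, the planned interim analysis included, and make sections 2 and 6 agree. There are two ways:
- Keep the relative endpoint, analyse the log value and report the back-transformed ratio as a percent difference. This is natural for vascular resistance.
- Redefine the endpoint in section 2 as absolute and use ANCOVA on the raw scale.

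Drop the rule that lets a normality check on the trial data choose the scale.

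The cost is wording in two sections and a little analysis work. Nothing needs measuring beyond the pairs that percent change already requires, and results can still be quoted in percent.

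A separate matter should be reconciled at the same time. Section 2 makes the 3-month echocardiogram, catheterization and walk test conditional on clinical indication, while these endpoints need a 3-month value from each patient. As written, complete pairs are not guaranteed and the 32-per-arm figures are optimistic. Resolving this may cost data collection, whichever analysis is chosen; the verdict here does not depend on it.

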Redfield et al, 2013 ¹⁰ double-blind, randomized, placebo- controlled	HFpEF	216 (113 sildenafil)	None	20 mg TIDx 12 weeks, followed by 60 mg TID for 12 weeks.	6 months	No improvement in exercise capacity or clinical status
Amin et al, 2013 ²⁰ double-blind, randomized, placebo- controlled	NYHA II/III EF<35%	106	None	25-50 mg TID	12 weeks	No improvement in exercise capacity or clinical status

1. Specific hypotheses

Phosphodiesterase- 5 inhibitors in heart failure with secondary reactive pulmonary hypertension improve exercise capacity, hemodynamic, echocardiographic parameters, and quality of life

2. Trial design

Patients over 18 years of age with HF who have PH by right heart catheterization (mean pulmonary artery pressure \geq 25 mm Hg, pulmonary capillary wedge pressure \geq 15 mm Hg, and pulmonary vascular resistance $>$ 3WU) will be eligible for randomization to sildenafil 20 mg, or placebo three times a day for 3 months. At baseline, a 6 minute walk test and quality of life questionnaire will be performed (Kansas City Cardiomyopathy Questionnaire) from 7 days prior to 3 days after qualifying right heart catheterization. If the echo was done for clinical indications within one month of enrollment, the data will be used. Laboratory tests are routinely obtained before right heart catheterization (comprehensive metabolic panel and NT-proBNP) and will be recorded for the study.

Participants will return for follow-up visits as needed for clinical indications. Our study coordinator will document changes of symptoms, changes in therapies, and capture clinical events like unscheduled hospital visits. For study purpose, the only follow-up visit will take place in 3 months. At that time, an echocardiogram, right heart catheterization, six minute walk, laboratory tests, and quality of life questionnaire will be repeated if clinically indicated. In addition, we will evaluate for signs and symptoms of HF (dyspnea, increased cough, paroxysmal nocturnal dyspnea, peripheral edema, S3 gallop, increased heart rate) at baseline and at the follow-up visit. These assessments are part of routine care for HF patients. The 3 month assessments should take place from 80-97 days following randomization whenever possible.

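### Quality of life is a stated secondary objective but has no listed outcome, no named KCCQ score and no assured 3-month measurement

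*Combined protocol and SAP*

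**What the plan says.** All references are to the combined protocol and SAP.

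- **Section 1, Specific hypotheses.** Phosphodiesterase-5 inhibitors are expected to "improve exercise capacity, hemodynamic, echocardiographic parameters, and quality of life".
- **Section 3, Secondary Objectives.** The trial is to determine whether sildenafil "can improve hemodynamics, right ventricular function, or quality of life".
- **Section 2, Trial design, baseline.** The instrument is named: "quality of life questionnaire will be performed (Kansas City Cardiomyopathy Questionnaire"), with a window from 7 days before to 3 days after the qualifying catheterization.
- **Section 2, Trial design, 3 months.** There is one study follow-up visit, with a target window of 80 to 97 days after randomization. At that visit, "laboratory tests, and quality of life questionnaire will be repeated if clinically indicated".
- **Section 2, outcomes.** The primary is 6 minute walk distance. The secondaries are "Percent of change of pulmonary arterial pressures (systolic, diastolic, and mean) and pulmonary vascular resistance from the baseline", the corresponding percent change in cardiac index, and "Percent of change in tricuspid annular plane systolic excursion".
- **Section 6, Statistical design.** "Primary and secondary endpoints are as noted above". A linear mixed model with a group contrast on change from baseline to 3 months is then planned for each outcome variable. Neither quality of life nor the KCCQ is mentioned.

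**The concern.** An objective needs an outcome that answers it. Here the protocol states a quality-of-life aim twice and names an instrument, but the chain stops before the outcome list.

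Three things follow if the plan is carried out as written:

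1. The quality-of-life objective has no listed endpoint, so a reader of the results could not tell from the plan whether a KCCQ comparison was meant to count as a secondary result.
2. No KCCQ score is named. The analyst could choose among scores after seeing the data.
3. The 3-month questionnaire depends on a clinical reason to repeat it. If that reason is related to how the patient is doing, the patients with a change score are a selected subset, and possibly a different subset in each arm.

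The objective is not incidental. The KCCQ is the only questionnaire in the study, and none of the six listed secondary variables can stand in for it. Table 1 of the protocol also cites a randomized, placebo-controlled sildenafil study, in patients selected on echocardiographic pulmonary pressure, as having improved quality of life. The sponsor thus has a stated reason to ask the question.

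**Working it through.** The point is one of correspondence between sections, so the main check sets them side by side.

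**Step 1. Match each stated aim to a listed outcome.**

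| Aim | Where stated | Listed outcome |
|---|---|---|
| Exercise capacity or tolerance | Section 1; Section 3, primary | 6 minute walk distance |
| Hemodynamics | Section 1; Section 3, secondary | Pulmonary arterial pressures, pulmonary vascular resistance, cardiac index |
| Echocardiographic parameters / right ventricular function | Section 1; Section 3, secondary | Tricuspid annular plane systolic excursion |
| Quality of life | Section 1; Section 3, secondary | None |

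The primary objective shows the form that is missing. It asks whether sildenafil "can improve exercise tolerance measured by 6 minute walk distance", so aim and measure stand together.

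**Step 2. Count.** Secondary variables: 3 pressures + 1 resistance + 1 cardiac index + 1 tricuspid annular excursion = 6. With the primary, 7. Quality-of-life variables among them: 0. One of three secondary objectives, and one of four parts of the hypothesis, has no endpoint.

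**Step 3. See whether Section 6 fills the gap.** It refers back for its endpoints and adds none. Its model applies to outcome variables in general and does not say that the KCCQ is one.

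**Step 4. Separate what is fixed for the KCCQ from what is open.** Fixed: the objective, the instrument, the baseline window, the visit window and a generic change-from-baseline model. Open: its status as an outcome, the score, the scale of change, and whether the 3-month value is obtained. Section 6 allows for imputation if attrition exceeds 10% in either group, but it introduces this under loss to follow-up. A patient who attends and is not given the questionnaire is not clearly covered.

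**Step 5. Confirm that the sample size is untouched.** Inputs from Section 6: 32 per arm, effect 0.7 SD, alpha 0.05. Sidedness is not stated; two-sided is assumed.

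- Normal approximation: 0.7 × √(32/2) = 2.80; 2.80 − 1.96 = 0.84; power = 79.96%.
- Noncentral t, 62 degrees of freedom, noncentrality 2.80: power = 78.7%.

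Both agree with the plan's figure of nearly 80%. Nothing in this point changes it.

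**Step 6. Illustrate what missing 3-month questionnaires would cost.** The documents give neither a KCCQ effect nor a completion rate. Assume, for illustration only, the same 0.7 SD effect and equal completion in both arms. Noncentrality is 0.7 × √(n/2), with 2n − 2 degrees of freedom:

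| Patients per arm with a 3-month KCCQ | Power |
|---|---|
| 32 (100%) | 78.7% |
| 28 (about 90%) | 73.0% |
| 24 (75%) | 66.1% |
| 16 (50%) | 48.3% |

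This shows loss of precision only. Bias from selective completion comes on top and cannot be sized from the documents.

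**Step 7. Size the multiplicity cost of one more secondary.** Section 6 describes no adjustment across secondary outcomes. If each is tested at 0.05, and if they were independent, the chance of at least one false positive is 1 − 0.95^6 = 26.5% for six variables and 1 − 0.95^7 = 30.2% for seven. The pressures are plainly correlated, so these figures are illustrative.

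**The case against.** The strongest reply is that the intent is clear and most of the analysis is already fixed in advance. The objective, the instrument and the visit are stated, and Section 6 gives a model with a contrast on change from baseline to 3 months. Its back-reference to endpoints follows both the outcome list and the Objectives section, so it could be taken to include the quality-of-life objective.

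Much of this stands. A reader might infer from the gap that the trial has no quality-of-life plan at all, or that any KCCQ result would be wholly post hoc. The documents do not support that: an analysis with a pre-stated objective, instrument, visit and generic model is better described as unlisted, with its score unspecified.

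What does not stand is that the gap is therefore harmless. The outcome list is the more natural referent for Section 6. Even on the generous reading, the Objectives section supplies only the words quality of life, with no score or measure of change.

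A second objection is that an added outcome line would not be enough. That is right. A reader might assume that the KCCQ is collected at both time points and that only the listing is missing, but collection is unconditional only at baseline. The opposite inference, that 3-month questionnaires will mostly be absent, is not supported either: the text makes the repeat conditional and gives no expected rate.

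A third is that the choice of KCCQ score and scale is not dictated by the documents. That also stands. The overall summary score is one reasonable choice; what matters is that one score is fixed in advance.

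Finally, the matter is secondary. That is accepted, and it limits the weight of the point.

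**Conclusion.** The point holds in a limited form. Quality of life appears in the hypothesis and is one of three secondary objectives, yet none of the seven listed outcome variables measures it, no KCCQ score is named, and the 3-month questionnaire is conditional. As written, the objective has no listed endpoint, the score could be chosen after the data are seen, and 3-month values may be selectively missing.

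The conclusion rests on reading Section 6 as referring to the outcome list, which is the more natural reading though not the only one. The lack of a named score and the conditional 3-month repeat do not depend on that reading. How many values would be missing, and in which direction that would bias a comparison, cannot be determined from the documents. The primary endpoint, the 64 patients and the stated power do not change. This should be corrected, but it does not threaten the main result.

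**What to change.** 1. Add one named KCCQ score to the secondary outcomes in Section 2, for example the overall summary score, defined as change from baseline to 3 months with its scale stated. Analyse it with the Section 6 mixed model by intention to treat.
2. In Section 2, make the 3-month KCCQ a study assessment for all randomized patients at the visit already planned, independent of clinical indication.
3. If step 2 is not done, remove quality of life from the hypothesis and the secondary objectives, so that the trial does not claim to answer a question for which it has not secured data.

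The cost is a few lines of text, one questionnaire per patient at an existing visit, and one more run of a model already planned. The downside is a seventh secondary variable without multiplicity control, so its result should be reported as supportive. No additional patients are needed.

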- Contraindication to sildenafil including need for nitric oxide donors such as organic nitrates or organic nitrates in any other form regularly and/or intermittently or current nitrate therapy
- History of primary PH, connective tissue disorders, severe COPD, pulmonary embolism, or left to right shunts
 - Primary (idiopathic) Pulmonary Hypertension in patients without history of heart failure
 - Pulmonary hypertension in patients with systemic scleroderma
 - Pulmonary hypertension due to congenital heart disease
 - Pulmonary hypertension due to severe COPD
 - Pulmonary hypertension in patients with systemic scleroderma
 - Pulmonary hypertension due to congenital heart disease
 - Pulmonary hypertension due to severe COPD or interstitial lung disease
- History of heart transplant, VAD, or any other solid organ transplant
- Likely to have solid organ transplant or any other major surgery during study enrollment/treatment period
- Liver cirrhosis as primary diagnosis

- History of massive pulmonary embolism
- Acute pulmonary embolism
- Female subject who is pregnant, breastfeeding, or one who is unwilling to practice an acceptable method of birth control unless postmenopausal or sterile.
- Unreliability as a study participant based on the investigator's (or designee's) knowledge of the subject (eg, alcohol or other substance abuse, inability, unwillingness to adhere to the protocol, documented non-compliance or vulnerable population
- Currently enrolled in another investigational drug or device clinical study, or less than 30 days since completing study
- Current diagnosis of HIV or AIDS
- End stage renal disease undergoing dialysis
- End stage liver disease
- Co-morbidities, if it limits exercise tolerance
 - morbid obesity (BMI>40)
 - COPD with oxygen dependence
 - severe peripheral vascular disease with intermittent claudication
 - status post amputation of lower extremity(s) at any level
 - severe degenerative joint disease preventing normal walking
 - CVA with long term sequella affecting ability to walk

5. Arms/regimens

6. Statistical design in detail (include one primary and any secondary endpoint(s), any stratification to be used in the randomization, sample size with power justification, analysis plan including plans for formal interim analysis, projected monthly accrual rate)

Sample size was calculated at 32 patients per arm, 64 patients total

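### Testing at 0.01 at the interim and at an unreduced 0.05 at the end gives an overall two-sided Type I error of about 0.055 if the interim can support an efficacy claim, and the plan does not say whether it can

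*Combined protocol and SAP*

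**What the plan says.** Everything on this point is in section 6 (statistical design) of the combined protocol and SAP.

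- **Timing:** the interim takes place "after data have been acquired for (approximately) 32 subjects", out of a planned 64.
- **Interim level:** it is run "using a temporary alpha of 0.01 to mitigate inflation of Type I error probability due to multiple testing".
- **Consequence:** results go to the Data Safety Monitoring Board, "which will advise the principal investigator on whether to continue with the study".
- **Final level and power:** "Planned sample size of 64 will provide nearly 80% power, using the final alpha of 0.05", for an outcome "for which the effect size is approximately 0.7".

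The section does not state whether tests are one- or two-sided, what overall error level is intended, which variable is tested at the interim, or what follows if the interim p-value falls below 0.01. It names no group-sequential boundary or spending function.

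**The concern.** A look that can stop only for futility or harm, or that only informs the Board, does not raise the chance of a false efficacy claim and needs no alpha for that purpose. The plan justifies its 0.01 by multiple testing and pairs a temporary alpha with a final one, which suggests that a positive interim could count as a result. On that reading there are two chances to reject, at 0.01 and then at the full 0.05, so the overall error must exceed 0.05. A strict interim level makes the excess small but does not remove it.

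Two things are at stake. A final p-value just under 0.05 could be called significant under a procedure whose error is above 5%. And if the interim p-value does fall below 0.01, its meaning would have to be settled after the data were seen. At the planned effect that is not a remote event: the interim alone would reject in about 24% of trials.

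**Working it through.** **Inputs, all from section 6.** Interim alpha 0.01; final alpha 0.05; interim at about 32 subjects; 32 per arm and 64 in total; 1:1 allocation; effect size 0.7. Sidedness is not stated and is inferred in step 1. The interim variable is not named; the calculation assumes one test, on the primary endpoint.

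**1. Reproduce the stated power.** The noncentrality is 0.7 × √(32/2) = 0.7 × 4 = 2.8.
- Normal approximation, two-sided 0.05: Φ(2.8 − 1.96) = Φ(0.84) = 80.0%.
- Noncentral t with 62 degrees of freedom, two-sided 0.05: 78.7%.
- Noncentral t, one-sided 0.05: 87.0%.

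The two-sided figures match the plan's nearly 80% and the one-sided figure does not. Two-sided testing is therefore the reasonable inference.

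**2. Overall Type I error as written, if the interim can support an efficacy claim.** The information fraction is t = 32/64 = 0.5. Under the null, Z1 (interim) and Z2 (final) are bivariate normal with correlation √t = 0.707. The overall error is 1 − P(|Z1| < 2.576 and |Z2| < 1.960).

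| Information fraction | Overall two-sided error | Final alpha that restores 0.05 with 0.01 at the interim |
|---|---|---|
| 0.4 | 0.0557 | 0.0441 |
| 0.5 | 0.0546 | 0.0452 (z = 2.003) |
| 0.6 | 0.0534 | 0.0464 |

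At t = 0.5 the excess is 0.0546 − 0.0500 = 0.0046. This is the share of null trials that would cross 0.01 at the interim but would not reach 0.05 at the end. The simple sum 0.01 + 0.05 = 0.06 is only an upper bound, because the two looks share half their data.

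**3. Small-sample check.** Two-sample t-tests were simulated under the null with 32 per arm at the end (20,000,000 runs each).
- 13 per arm at the interim (26 subjects): 0.0560.
- 16 per arm (32 subjects): 0.0550.
- 19 per arm (38 subjects): 0.0539.
- 16 per arm, with the final alpha lowered to 0.045: 0.0502.

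**4. Sensitivity to sidedness.** If both levels were one-sided, the overall error at t = 0.5 would be 0.0538. The excess does not depend on the two-sided inference.

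**5. Power at effect size 0.7** (t-tests, 32 per arm; the two-look figures are from 7,500,000 simulated trials).
- Final test alone: 78.7% at 0.05.
- Both looks counted, 0.01 then 0.05: 79.1%.
- Both looks counted, 0.01 then 0.045: 77.8%.

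The cost of lowering the final alpha to 0.045 is 79.1 − 77.8 = 1.3 percentage points.

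**The case against.** The strongest reply is that 0.055 depends on a rule the plan never writes. The only stated consequence of the interim is advice on continuing. If that advice can lead to stopping only for futility or harm, or never to an efficacy claim, the final 0.05 is sound. The plan also says that it mitigates inflation; it does not claim full control and names no overall level. Nothing in it is miscalculated, its power figure reproduces, and the excess is only about half a percentage point.

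All of this stands, and it limits the size of the point. It does not remove it. Nothing elsewhere in the document says what crossing 0.01 permits, and the plan's own reason for choosing 0.01 makes sense only if the interim can contribute to an efficacy conclusion. That the Board is advisory does not settle whether a trial stopped after crossing 0.01 would be reported as positive.

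Two narrower objections are also fair. The value 0.045 is approximate, since simulation puts the overall error at 0.0502 with it. And the final alpha is not the only place to make the correction, since a much stricter interim level would also nearly restore 0.05.

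**Conclusion.** The concern holds, as a small but real defect. If crossing 0.01 can support an efficacy claim, the 0.01/0.05 pair has an overall two-sided Type I error of about 0.055: 0.0546 by the normal calculation and 0.0550 by t-test simulation. It runs from 0.0534 to 0.0560 across the two methods if the interim falls between roughly 40% and 60% of the information. If no such claim is allowed, the error does not exceed 0.05.

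The figure assumes two-sided tests (inferred from the power statement) and a single endpoint tested at both looks. If the correction is made at the final test, it changes the conclusion only for a final p-value between about 0.045 and 0.05. The power statement is not wrong as written. The main gap is the unwritten interim rule, because without it a reader cannot tell whether 0.05 at the end is correct. It should be fixed before any interim data are seen.

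**What to change.** In section 6, state that tests are two-sided and whether crossing 0.01 on 6 minute walk distance at the interim allows an efficacy claim. Then take one of two routes.

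- **Efficacy claim allowed.** Keep 0.01 at the interim and set the final two-sided alpha to about 0.045, solved again at the actual interim fraction because the plan gives only an approximate count. Restate power as about 78%, counting both looks.
- **No efficacy claim allowed.** Say so. The final 0.05 may then stand.

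Two alternatives serve the first route. An interim level of 0.001 with 0.05 at the end gives an overall 0.0502 and leaves the final level essentially intact. If a Lan-DeMets O'Brien-Fleming-type function is preferred, the plan should name the convention. At half information the two-sided levels are about 0.0031 and 0.0490 with 0.025 spent per side, or about 0.0056 and 0.0478 with two-sided 0.05 in the function.

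The change is to wording only and needs no extra patients. Lowering the final alpha to 0.045 costs about 1.3 percentage points of two-look power (79.1% to 77.8%). Declaring that the interim allows no efficacy claim costs nothing against the 78.7% power of the final test alone.
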